7.1.2 Secondary Outcome Measures

- 1] Adverse Events (AEs) – within 4 weeks of treatment as judged by **blinded** physician reviewers to be possibly related to the study drug(s) using the same criteria as in the Phase 1 study.
- 2] Parasite clearance time – from the initiation of treatment to the first of 2 successive negative smears.
- 3] Time to recrudescence or reinfection – time from the initiation of treatment to the reappearance of asexual *P. falciparum* parasites on the thick smear.
- 4] Effects on the QT (QTc) interval – mean changes from the baseline pre-treatment QT (QTc) interval to the post-treatment QT (QTc) interval after treatment with AQ-13 or Coartem.
- 5] Pharmacokinetic parameters for AQ-13 – these will include measurements of AQ-13 blood levels over time (peak levels, AUC, MRT), drug distribution (Vd/F) and drug elimination ($t\frac{1}{2}$, Cl/F).
- 6] Fever clearance time: Time in hours from the initiation of therapy until disappearance of fever for at least 24 hours.

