2.3 Potential Risks and Benefits

2.3.1 Potential Risks

Immediate (Short-Term) Risks. The first potential risk of participation in this study is that the investigational drug AQ-13 may not work; it may not cure uncomplicated *P. falciparum* malaria in Malian adults. If AQ-13 does not clear malaria parasites from subjects' blood by day 7 in the AQ-13 arm, those subjects will be treated with Quinine. In addition, if Coartem does not clear malaria parasites from subjects' blood in the Coartem control arm by day 7, these subjects will also be treated with Quinine, which is recommended in Mali for rescue in persons who fail treatment for uncomplicated malaria.

The most frequent side effects of AQ-13 in the volunteers who received it during the Phase 1 studies (and therefore the most likely adverse events (AEs) in these Proof of Concept studies) are similar to those of CQ: they include headache, dizziness, and digestive tract symptoms (nausea, loss of appetite, diarrhea, vomiting and abdominal pain). One of 126 subjects developed a mild, transient rash on her lower body, and 1 had muscle damage for several days, which is thought not to have been caused by the study drug, and is often caused by vigorous exercise. Other potential risks include bleeding, bruising, discomfort, black and blue spots and infection from venipunctures to obtain blood specimens. Abnormal beating of the heart is a potential risk, and has been observed in two subjects during the previous studies. Although it is thought not to have been caused by the study drug, the study drug will be stopped and subjects will be treated with quinine if they have abnormal beating of the heart and were randomized to AQ-13.

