5.2 Eligibility (Inclusion/Exclusion) Criteria

Inclusion criteria for this study include:

- 1] Adult Malian males ≥ 18 years of age,
- 2] Uncomplicated malaria with $\geq 2,000$ asexual *P. falciparum* parasites per μl , and
- 3] Informed consent obtained and signed.

After obtaining the initial consent to treat, a physical examination and medical history will be obtained and recorded on a standard form. Thick smears will be obtained to diagnose *P. falciparum* infection. Patients who fulfill the first two criteria above will be invited to participate in the study, and informed consent will be obtained from those who choose to participate.

Exclusion criteria for this study include:

- 1] Severe or complicated malaria (including temperatures $\geq 40^\circ \text{C}$),
- 2] $\geq 100,000$ asexual parasites per μl of blood,
- 3] Anemia or other laboratory results (other than malaria) that require treatment (e.g., Hb ≤ 7 gm/dL, K $^+$ ≤ 3.5 mM, BP $\geq 140/90$),
- 4] Seizures or impaired consciousness,
- 5] Recent antimalarial treatment by history (within ≤ 2 weeks),
- 6] Chronic medications (including CYP3A4 inducers such as rifampin and nevirapine),
- 7] Ventricular or atrial arrhythmias including frequent ventricular premature beats or extrasystoles (> 20 per hour) or second or third degree heart block on the screening Holter recording,
- 8] Infection with other plasmodial species on the blood smear (*P. ovale*, *P. ovale*, *P. vivax*).

Enrollment and randomization will occur only after a final review to ensure that all of the inclusion criteria

have been met and that none of the exclusionary criteria are present.

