6.2.2 Special Assays or Procedures

Prior to treatment with AQ-13 or Coartem, subjects will have a 1 hour baseline Holter recording to exclude pre-existing arrhythmias and other cardiac abnormalities and a baseline eye examination to ensure that there are no pre-existing ocular abnormalities before treatment or any new ocular abnormalities (potential AEs) after treatment. Randomization will be performed after the chemistry, hematology, eye and Holter recording results have been checked to ensure there are no criteria for exclusion and that informed consent to participate has been obtained and signed. Special assays or procedures that will be used in these studies include:

- PCR testing for parasite genotypes and for the K76T point mutation in *pfCRT* (Mali; SOP),
- Fluorescence HPLC assay for AQ-13 and its metabolites (New Orleans; SOP),
- Holter recordings for evidence of arrhythmias (Mali and New Orleans; SOP),
- Eye examinations pre- and post-treatment to test for evidence of keratopathy, retinopathy, other pre-existing abnormalities or treatment-related ocular side effects (adverse events) (Mali; SOP),
- Pharmacokinetic analysis of AQ-13 drug and metabolite blood and urine levels (Mali and New Orleans; SOPs for AQ-13 HPLC, CRFs for Out-Patient Follow-Up).

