6.5 Inpatient Period

Blood samples will be taken for drug and metabolite levels on days 1-5 and hematology and chemistry panels on day 4. After screening Holter recordings have been obtained and reviewed for pre-existing arrhythmias, continuous 24 hour Holter recordings will be performed on each of days 1-4 (focusing on the time between 2 and 6 hours after dosing for maximal effects on the QT interval). Urine collections will be performed on each of days 1-4. An eye exam plus an additional 1 hour Holter recording will be performed at the end of week 1.

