10 STATISTICAL CONSIDERATIONS

10.1 Study Outcome Measures

The primary, secondary and tertiary objectives (Section 3, above) and outcome measures (Section 8, above) in this study will be assessed statistically as outlined below (Table 7).

Table 7.

Statistical Assessment of Study Endpoints

COMPONENTS OF THE PRIMARY ENDPOINT

- Lack of recrudescence at 42 days
- < 25% of baseline asexual parasitemia on day 3
- Clearance of asexual parasitemia and fever by day 7

STATISTICAL TESTS

- Pearson χ^2 , Fisher Exact test
- Pearson χ^2 , Fisher Exact test
- Pearson χ^2 , Fisher Exact test

SECONDARY ENDPOINTS

- Adverse Events (AEs) Pearson χ^2 , Fisher Exact test
- Effects on the QT (QTc) Interval (within individuals) Wilcoxon, Friedman test
- Effects on the QT (QTc) Interval (between groups) ANOVA, Kruskal-Wallis test
- Pharmacokinetic Parameters for Parent Compounds (AUC_t, t_{1/2}, Vd/F, Cl/F, MRT) Mann-Whitney, Kruskal-Wallis
- Time to parasite Clearance, Recrudescence or Reinfection (between groups) Kaplan-Meier, Cox Hazard
- Time to fever clearance (between groups) Kaplan-Meier, Cox Hazard

TERTIARY ENDPOINTS

- Pharmacokinetics of metabolites as above
- Aminoquinoline (chloroquine) pruritus Fisher Exact test

AUC_t = total area under the curve; t_{1/2} = elimination half-life; Cl/F = oral clearance; Vd/F = oral apparent volume of distribution; MRT = mean residence time.

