Times to recrudescence and reinfection will be analyzed using life tables, and compared using the log rank test. Cox regression will be used to compare multiple (multivariate) predictors of times to recrudescence and reinfection. Pharmacokinetic parameters will be examined for AQ-13 doses and compared to data from the Phase 1 studies, as appropriate. **Using the same protocol as in the Phase 1 study [11], the relatedness of adverse events (AEs) to study drugs will be classified independently by two blinded physicians according to the definitions in section 8.3 on page 30 as unknown, not related, unlikely to be related, or possibly, probably or definitely related to the study drugs, based on temporal relationships and biological plausibility.** The frequencies of AEs will be compared between AQ-13 and Coartem using Pearson Chi-square. Because more than one AE may occur in an individual patient, the proportion of patients receiving AQ-13 with AEs will be compared with Coartem using Chi-square or the Fisher Exact test. The severity of AEs will be classified using the recent FDA Guidance for Healthy Adult and Adolescent Volunteers in Preventive Vaccine Trials [23], and the severity of AEs across the study arms will be compared using Chi-square. QT interval corrections for heart rate (QTc) will be made using both Bazett's and Fridericia's formulas [41-42]. Within-patient maximum changes from baseline will be assessed using the Wilcoxon test for paired observations. Between-group QT interval changes will be compared using ANOVA or Kruskal-Wallis.

HYPOTHESES BEING TESTED.

The primary hypothesis is that the efficacy of AQ-13 for uncomplicated *P. falciparum* malaria is similar to

that of Coartem - based on a non-inferiority margin of 15%. That is, that AQ-13 will produce a cure rate within 15% of the Coartem control (standard). The secondary hypothesis is that AQ-13 will have safety profiles in subjects with uncomplicated malaria comparable to those for AQ-13 in healthy volunteers [11].

EXPECTED OUTCOMES.

Our preliminary (previous) studies have shown that AQ-13 is:

- *active in vitro* against CQ-resistant and multi-resistant *P. falciparum* [8-9],
- *active in vivo* against CQ-resistant *P. falciparum* in the squirrel monkey model of human infection with CQ-resistant *P. falciparum* (enclosed Figures 1 and 2 in the Appendix), and
- *safe in human subjects* based on Phase 1 studies recently performed in New Orleans [11].

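### The plan has no by-arm count of men with marked QTc prolongation or new Holter arrhythmia, and does not say whether mean or maximum QT change is compared between arms

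*Combined protocol and SAP*

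**What the plan says.** **QT endpoint and tests.** Section 7.1.2 item 4 defines the endpoint as "mean changes from the baseline pre-treatment QT (QTc) interval to the post-treatment QT (QTc) interval after treatment with AQ-13 or Coartem"; the synopsis and Section 3 also define it as a mean change. Table 7 (Section 10.1) lists "Effects on the QT (QTc) Interval (between groups) ANOVA, Kruskal-Wallis test", with Wilcoxon and Friedman tests within individuals. Section 10.3 corrects QT by both Bazett and Fridericia and then says: "Within-patient maximum changes from baseline will be assessed using the Wilcoxon test for paired observations". The next sentence is: "Between-group QT interval changes will be compared using ANOVA or Kruskal-Wallis".

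**Recordings.** Section 6.5 states that "continuous 24 hour Holter recordings will be performed on each of days 1-4 (focusing on the time between 2 and 6 hours after dosing"), which is 4 × 24 = 96 hours per man, besides short recordings at screening and at weeks 1 and 2. Section 6.2.2 gives the purpose: "Holter recordings for evidence of arrhythmias (Mali and New Orleans; SOP").

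**Why the heart is watched.** Section 2.3.1 says: "Abnormal beating of the heart is a potential risk, and has been observed in two subjects during the previous studies". It adds that the study drug was not thought to be the cause. Exclusion criterion 7 (Section 5.2) keeps out men with arrhythmias, including "frequent ventricular premature beats or extrasystoles (> 20 per hour"), or with second or third degree block at screening.

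**How an arrhythmia is handled.** Cardiologists in both countries read the Holters (Section 6.2.3.2), and Table 9 provides for grading Holter adverse events. Section 6.8 lists new ventricular tachyarrhythmia or heart block as a reason to discontinue treatment. Section 10.3 compares adverse event frequencies, the proportion of men with events, and severity between arms. The adverse event endpoint in Section 7.1.2 item 1 covers events judged possibly related, and the halting rules in Table 4 require a probable or definite relation.

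**The concern.** Cardiac harm from a drug of this kind may show as a large QTc increase or a new rhythm disturbance in a few men while most are unaffected. ANOVA and Kruskal-Wallis ask whether one arm as a whole lies higher than the other. The paired Wilcoxon test on maximum changes asks whether men as a group rose from baseline. None of these reports how many men, in which arm, had a marked increase.

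The adverse event route covers this only in part. Section 10.3 plans overall tests of events and of men with events, with no cardiac category. An arrhythmia judged unrelated, as the two earlier cases were, would fall outside the endpoint in Section 7.1.2. No QTc value is given at which prolongation without symptoms becomes an adverse event.

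The sponsor expects the trial to show that AQ-13 is safe (end of Section 10.3). A non-significant QT comparison could be cited in support while a few markedly prolonged men appear in no planned table.

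**Working it through.** **Inputs.** The documents give 33 men per arm (Section 10.2; Table 8's 26 / 0.8 = 32.5, rounded up). They give no SD, effect size, power or significance level for QT, so there is no planned QT figure to reproduce. Assumed here: SD of QTc change 15 to 25 ms; one to three AQ-13 men raised by 60 to 80 ms; no effect in any other man; an illustrative analysis cut-off of 60 ms; two-sided 5% tests.

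**Step 1. Movement of the arm mean.** With k affected men, the shift is k × increase / 33.
- Smallest: 1 × 60 / 33 = 1.8 ms.
- Largest: 3 × 80 / 33 = 7.3 ms.

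**Step 2. Mean difference detectable with 80% power.** (1.96 + 0.84) × SD × √(2/33), where √(2/33) = 0.246.
- SD 15 ms: 10.3 ms. SD 20 ms: 13.8 ms. SD 25 ms: 17.2 ms.

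Every shift in step 1 is below every value here.

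**Step 3. Simulated chance of a significant between-arm test.** For one to three affected men, ANOVA is significant in about 5 to 16% of trials and Kruskal-Wallis in about 4 to 9%. With 28 evaluable men per arm (Section 5.1) the largest shift is 3 × 80 / 28 = 8.6 ms, and the results are similar: about 5 to 18% and 4 to 9%.

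**Step 4. What a count can and cannot do.** For k men against 0, with 33 per arm, the two-sided Fisher p is 2 × C(33,k) / C(66,k).

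| Men above cut-off | Fisher p |
|---|---|
| 2 vs 0 | 0.49 |
| 3 vs 0 | 0.24 |
| 5 vs 0 | 0.053 |
| 6 vs 0 | 0.024 |

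Significance needs 6 vs 0 (uncorrected Pearson chi-square: 4 vs 0, p = 0.039). A count does show that affected men exist. At a true rate of 5% the chance of at least one among 33 is 1 − 0.95^33 = 82%; at 10% it is 97%. It also carries its own uncertainty: 3/33 is 9%, exact 95% interval 2 to 24%. For 0/33 the one-sided 95% upper bound is 1 − 0.05^(1/33) = 8.7%.

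**Step 5. Chance flags.** At SD 20 ms, an unaffected man's single reading exceeds 60 ms (3 SD) with probability 0.00135. The chance of at least one such man among 33 on Coartem is 1 − (1 − 0.00135)^33 = 4%. If each man's largest of four independent readings is used, the exponent is 132 and the chance is 16%. At SD 25 ms the same two figures are 24% and 66%. Correlation between readings would lower the four-reading figures.

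**The case against.** **The plan looks beyond the average.** A reader might infer that QT is analysed only as an average. That is wrong: Section 10.3 takes each man's maximum change, and recording concentrates on the hours when the largest effect is expected. What remains is that the maximum is tested only within men, and the between-arm sentence leaves its measure open.

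**Arrhythmias are not averaged away.** A reader might also infer that they are lost in a mean. They never enter the QT mean: they are read, graded, compared as adverse events, and can lead to discontinuation or a halt. Section 10.3's event comparisons do not repeat the relatedness limit of Section 7.1.2, and nothing forbids a separate cardiac table. This stands. The gap is that no such table is specified and that symptomless QTc prolongation has no stated entry point.

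**A count is no more powerful.** It is tempting to set the low chance of a significant ANOVA against the high chance of seeing at least one flagged man, but one is a test result and the other is visibility. Compared like with like, the count does worse: if each AQ-13 man has a 10% chance of an 80 ms increase (SD 20 ms), ANOVA is significant in about 21% of trials and Fisher's test on the count in about 6%. This also stands. The main limit is 33 men per arm.

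**The scenario is assumed.** If AQ-13 raised QTc in most men, a comparison of means or ranks would be the right tool. That is a reason to keep those tests and put the count beside them.

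**Conclusion.** The point holds as a cheap improvement to a secondary safety analysis. Sections 7.1.2 and 10.3 differ on the QT measure, and the between-arm test does not say which applies. No QTc threshold count or Holter arrhythmia outcome is planned by arm. Under the stated assumptions, one to three affected men move the mean by about 2 to 7 ms, and the planned between-arm tests would be non-significant in roughly 84 to 96% of trials. The size depends on the assumed SD and increase; the absence of a count and the unclear measure do not.

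The documents do not support a forecast that the trial will report no cardiac difference because of averaging. With so few men, a test on counts would usually be non-significant too. Nor do they show that AQ-13 causes arrhythmia. The supported conclusion is narrower: as written, the plan lets a null QT test stand without showing how many men had a marked change.

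**What to change.** 1. **Reconcile the measure.** Make Section 7.1.2 item 4, Table 7 and Section 10.3 agree on whether mean or maximum change is compared between arms, and under which rate correction.
2. **Add descriptive counts.** In Section 7.1.2 item 4 and Table 7, report for each arm the number and proportion of men (a) whose QTc increase, or absolute QTc, exceeds an analysis cut-off fixed before unblinding, and (b) who have a new Holter abnormality of the kind listed in exclusion criterion 7, whatever its judged relatedness. Give each an exact 95% interval. Fix in advance how a man's readings are combined, so that noise in a maximum over many readings does not create false flags.
3. **Limit the inference.** State that a non-significant QTc difference does not by itself support a conclusion of cardiac safety.

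The cut-offs serve the analysis only and set no stopping or treatment rule.

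The cost is wording and one table, using recordings already planned, with no added visits or men. The downside is wide intervals and some chance flags in either arm, which the report should acknowledge.

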7.1.3 Tertiary Outcome Measures

- 1] Pharmacokinetics of AQ-13 metabolites – estimates of pharmacokinetic parameters for the mono- and di-*N*-dealkylated metabolites of AQ-13 (AQ-72, AQ-73).
- 2] Aminoquinoline (CQ) pruritus – pruritus in persons receiving AQ-13 or Coartem, especially in persons with a history of pruritus after treatment with CQ.

7.2 Assessment of Treatment Outcomes

7.2.1 Parasitologic Data

Asexual parasite counts (parasite densities per μl of blood) will be based on the average of two independent readings for each time point – performed by two independent microscopists (both blinded to the treatment the patient received). Blood smears will be obtained beginning at the time of enrollment and continuing twice daily (every 12 hours) until two successive smears are negative during the week-long (6-7 day) inpatient stay. After the patient has been discharged, two thick smears will be obtained at each of the twice weekly follow-up appointments during weeks 2 to 6 (Gantt Chart on page 27).

Laboratory Procedures: Parasite counts will be obtained by examining Giemsa-stained thick blood smears containing a minimum of 300 white blood cells and multiplying the number of asexual parasites observed by 25 to estimate the parasite count based on a white blood cell count of 7,500 white cells per μl of blood.

Quality Control: Slides for which the parasite densities estimated by the two microscopists vary by more than 20% or differ qualitatively (negative vs. positive, presence vs. absence of species other than *P. falciparum*) will be examined by a third senior microscopist to resolve those questions.

Parasitologic Outcomes that will be assessed and compared between the two study arms will include:

- Reduction of asexual parasitemia to < 25% of the admission parasite count by day 3,
- Clearance of asexual parasites from the blood on or before day 7 after treatment, and
- Recurrent asexual stage parasitemia on or before day 42.

Assessment and Reporting of Parasitologic Outcomes

Based on the parasitologic data, the PI and one physician colleague (both blinded to the treatment the patients received) will assess the parasitologic outcomes for each of the participants. Those data will then be summarized by the subject's study numbers and returned to the study statistician who will place the data in groups by study arm (retaining blindedness by using Arm 1 and Arm 2 to identify the study arm rather than AQ-13 and Coartem) before the data are tested for differences and presented to the DSMB.

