Safety Oversight will be assisted by a Data Safety and Monitoring Board (see section 8.7 on page 33, below).

Flow Chart 2

PROOF OF CONCEPT STUDY FOR AQ-13 ADULT MALES WITH UNCOMPLICATED *P. falciparum* MALARIA

Recruitment in the Villages of Missira and Sirakoroba in Northwestern Mali
and from Outpatient Referral Clinics in the city of Bamako;

In-Patient Studies at the Clinical Research Center, Hôpital Point G in Bamako

Flow Chart 3**PROOF OF CONCEPT STUDY FOR AQ-13
RANDOMIZATION, DRUG ADMINISTRATION AND FOLLOW-UP**

Recruitment in the Villages of Missira and Sirakoroba in Northwestern Mali

and from Outpatient Referral Clinics in the city of Bamako;

In-Patient Studies at the Clinical Research Center, Hôpital Point G in Bamako

EYE EXAMS, HOLTER RECORDINGS, CHEMISTRY PANEL, HEMATOLOGY (CBC)
(n=70; 35 each for the AQ-13 and Coartem groups, expected 5% ineligible).

•INCLUSION CRITERIA:

≥ 2,000 asexual *P. falciparum* parasites per μ l,
Uncomplicated *P. falciparum* malaria,

•Baseline Screening Holter Recording x 1 hour,**•Visual Screening** baseline acuity, visual fields,**•EXCLUSIONS:** Hb ≤ 7 gms/dL, K+ ≤ 3.5 mEq/L, arrhythmias, heart block, BP ≥ 140/90 or severe or complicated malaria.

RANDOMIZE ELIGIBLE ADULT VOLUNTEERS WITH UNCOMPLICATED *P. falciparum* MALARIA
(n=66; 33 each for the AQ-13 and Coartem groups, expected 20% loss to follow-up).

•Filter Paper Blots for molecular studies,**•Freeze Initial Parasites** at -70° C,**•pfcr PCR and other Tests** for CQ Resistance,**•Oral Administration of 700 mg AQ-13 on days 1-2,** followed by 350 mg on day 3, OR

Oral Administration of Coartem, 80 mg artemether

+ 480 mg lumefantrine twice daily x 3 days,

•Repeat Daily Blood Smears (days 1 through 7), repeat Hematology, Chemistry panels on day 4,**•AQ Drug and Metabolite Levels** at 0, 0.5, 1, 2, 4, 6, 12, 18, 24, 24.5, 25, 26, 28, 30, 36, 48, 48.5, 49, 50, 52, 54, 60, 72, 96 and 120 hours x 5 ml,**•Holter Monitoring** 24 hours/day x 4 inpatient days,**•One Week** eye exam, 1 hour Holter recording,**•WITHDRAWAL:** severe or complicated malaria.

FOLLOW-UP
for a total of 6 weeks,
PRIMARY ENDPOINT is
a lack of recrudescence
with the same genotype(s)
(n=28 evaluable subjects/group)

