6.6 Follow-up and Final Visits, if applicable

After completion of the 5-7 day inpatient stay (Flow Chart 4 below, and Table 1, above), there are 2 follow-up outpatient visits each week for the next 5 weeks (total of 6 weeks active involvement in the study). At each of the follow-up visits during Weeks 3-6, a blood sample is obtained for AQ-13 drug and metabolite blood levels to define the pharmacokinetics of AQ-13 and its metabolites. In addition, there is a final 1 hour Holter recording at the 2 week follow-up visit plus an in-depth interview about potential AEs.

Sequence of Events during the Follow-Up Outpatient Visits. The twice-weekly follow-up outpatient visits will include (in sequence): an interval history with discussion of potential AEs related to study drugs, review of current medications and a physical examination with recorded results for vital signs (blood pressure, heart rate, respiratory rate, temperature), conjunctival pallor, pulmonary, cardiac and abdominal examinations (including splenomegaly) (see the Out-Patient Follow-Up CRFs).

Allowable Windows (Times) for Follow-Up Outpatient Visits. The major purposes of the follow-up outpatient visits are to: 1] follow the pharmacokinetics of AQ-13 and its metabolites over time to estimate the terminal elimination $t_{1/2}$ and other pharmacokinetic parameters for AQ-13 and its metabolites in subjects with uncomplicated malaria and 2] to test for recurrent infection by distinguishing new infections (which do not represent recurrences or treatment failures) from recrudescences of infection with the same parasite genotypes (which do potentially represent treatment failures). Although the best data (in terms of points on the time-concentration curve to estimate the pharmacokinetic parameters) are provided by twice-weekly follow-up blood samples during the first two weeks (Weeks 1 and 2), the software that will be used for this purpose (PharSight) can adjust and still provide reasonable estimates of the relevant pharmacokinetic parameters no matter what the time points are. For this reason and because recurrent infection should be detected as soon as possible, late return visits will be permitted up to the final 6 week (42 day) time point.

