7.1.1 Primary Outcome Measures

Cure is a lack of recrudescence within 42 days (PCR-corrected) – no evidence of recrudescence with the same parasite genotype(s) after reduction of the asexual parasitemia to less than 25% of the admission value by day 3 and clearance of asexual parasites and fever by day 7. Failure is defined as “lack of cure”.

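### Inpatient smears are 12-hourly until two negatives in section 7.2.1 but daily through day 7 in Flow Chart 3, which affects the resolution of parasite clearance time and the dating of early reappearance

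*Combined protocol and SAP*

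**What the plan says.** Section 7.2.1 (Parasitologic Data) starts smears at enrollment, "continuing twice daily (every 12 hours) until two successive smears are negative during the week-long (6-7 day) inpatient stay". Flow Chart 3 in section 4 gives a different rule: "Repeat Daily Blood Smears (days 1 through 7), repeat Hematology, Chemistry panels on day 4". The Gantt Chart has an X for the thick smear on each of inpatient days 1 to 7. Flow Chart 4, which sets out the timed procedures from screening onward, has no row for smears.

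The endpoints that use these smears are:

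- Parasite clearance time, a secondary endpoint (section 7.1.2), runs "from the initiation of treatment to the first of 2 successive negative smears". Table 7 in section 10.1 plans "Time to parasite Clearance, Recrudescence or Reinfection (between groups) Kaplan-Meier, Cox Hazard".
- Cure, the primary endpoint (section 7.1.1), includes "clearance of asexual parasites and fever by day 7". Section 7.2.1 words the parasite part as "Clearance of asexual parasites from the blood on or before day 7 after treatment".
- Time to recrudescence or reinfection, also secondary (section 7.1.2), ends when asexual parasites are seen again on the thick smear.

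The length of the inpatient stay also varies. Section 7.2.1 has 6 to 7 days, while section 6.6 says "After completion of the 5-7 day inpatient stay" and section 5.1 likewise allows 5 to 7 days.

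**The concern.** The two rules differ in how often smears are taken and in when they stop. Site staff cannot tell from the documents which applies, and the work sheet that might settle it is silent.

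Each rule, followed alone, has its own weakness. Daily smears double the interval in which clearance can be observed. The stopping rule ends inpatient smears for a man as soon as he has two negatives, so nothing is scheduled to detect or date parasites that come back before his first outpatient visit. If different men are followed under different rules, clearance time is also not measured on one scale across the trial. At stake are the precision of one secondary endpoint and the onset dates, and occasionally the detection, of early reappearance.

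**Working it through.** No sample size, power or alpha in the plan depends on the smear interval, so there is no stated figure to reproduce.

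**1. Resolution of clearance time.** With smears every g hours and true clearance at T hours, the first negative smear is at ceil(T/g) × g. If T is uniform within an interval (an assumption), the mean delay is g/2 and the grouping SD is g/√12.

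- g = 12 h: mean delay 12/2 = 6 h; SD 12/√12 = 3.5 h; maximum 12 h.
- g = 24 h: mean delay 24/2 = 12 h; SD 24/√12 = 6.9 h; maximum 24 h.

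**2. When inpatient smears end.** Time 0 is the start of day 1, so day 7 begins at 144 h and day 8 at 168 h. Under section 7.2.1 the second negative is the last inpatient smear. The last column is 168 h minus that time.

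| True clearance | 12-hourly: first / second negative | Daily: first / second negative | 12-hourly rule: last smear to start of day 8 |
|---|---|---|---|
| just after 24 h | 36 / 48 h | 48 / 72 h | 120 h |
| just after 36 h | 48 / 60 h | 48 / 72 h | 108 h |
| just after 48 h | 60 / 72 h | 72 / 96 h | 96 h |
| just after 72 h | 84 / 96 h | 96 / 120 h | 72 h |

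A man negative at 36 h and 48 h therefore has at least 120 h (5 days) without a planned smear. The gap is longer if his first week-2 visit falls after day 8. A man without two successive negatives goes on being smeared every 12 h while he is an inpatient.

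**3. What the coarser interval could cost.** The documents give no distribution of clearance times, so this is illustrative. The simulation used lognormal times, 28 men per arm (the evaluable target in section 5.1), a two-sided rank test at 0.05 and 2,000 runs per setting.

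| Assumed medians, log-SD | Exact times | 12 h steps | 24 h steps |
|---|---|---|---|
| 36 vs 42 h, 0.3 | 0.46 | 0.43 | 0.34 |
| 36 vs 48 h, 0.3 | 0.93 | 0.91 | 0.85 |
| 36 vs 48 h, 0.5 | 0.55 | 0.54 | 0.52 |
| 48 vs 60 h, 0.3 | 0.77 | 0.75 | 0.70 |

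Across all ten settings tried at 28 per arm, going from 12 h to 24 h steps lost about 1 to 9 points of power.

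**4. Length of stay.** A man discharged on day 5 or 6, which sections 5.1 and 6.6 allow, has no inpatient smear on day 7 under either rule.

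**The case against.** Three stronger readings are tempting, and the documents do not support them.

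A reader might infer that day-7 status goes unread under section 7.2.1. It does not. The criterion is clearance by, or on or before, day 7, not the result of a smear taken on day 7. A man with two successive negatives at 36 and 48 h has met the parasite part, and men who have not cleared are still being smeared.

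A reader might infer that cure is misclassified. Same-genotype parasites that return on days 4 to 7 and persist are found at the twice-weekly visits, where section 7.2.1 takes two thick smears, and they still count as recrudescence within 42 days. Only parasitemia that comes and goes before week 2 would escape, and the documents give no rate for that.

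A reader might infer that the contrast between arms depends on the schedule, or that daily smears are simply too coarse. Either schedule would apply to both arms and the microscopists are blinded. Under the uniform assumption the mean delay is the same in each arm and cancels from the difference. What remains is lost precision on an endpoint for which the plan sets no precision and claims no power.

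It is also fair to say that the Gantt Chart does not contradict 12-hourly smears. Its X is not a count, since its pharmacokinetics row uses numbers where counts are meant. It does contradict stopping early. Two of the three schedules already run to day 7, which makes joining the rules easy. No text does so.

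**Conclusion.** The point holds as a conflict in current text with modest consequences. Sections 4 and 7.2.1 give inpatient smear rules that differ in frequency and stopping point, and they must be reconciled.

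Under the daily rule, grouping SD for clearance time is 6.9 h rather than 3.5 h and mean delay is 12 h rather than 6 h, assuming clearance is uniform within an interval. The corresponding power loss of about 1 to 9 points rests on assumed clearance times and spreads and on a rank test standing in for the planned survival methods. Under the stopping rule, an early clearer can go 5 days or more without a planned smear. Reappearance in that gap is dated late, or missed if transient; how often is unknown. Classification of clearance by day 7 is not undermined, and the sample size is not affected.

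**What to change.** State one assessment schedule in section 7.2.1, Flow Chart 3, the Gantt Chart and a new smear row in Flow Chart 4: every 12 hours until two successive negatives, then once daily through day 7. Take parasite clearance time from the 12-hourly smears. Use the later daily smears to detect and date early reappearance. Leave the definition of clearance by day 7 unchanged: tying that component to a day-7 smear would redefine part of the primary endpoint and make men without that slide missing.

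Reconcile the length of the inpatient stay between sections 5.1, 6.6 and 7.2.1 so that the schedule can be carried out to day 7.

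The cost is protocol wording, one work-sheet row, and a few more slides per man than under section 7.2.1 alone. The change joins two rules already in the protocol and concerns assessment only, not treatment.
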